10.4.3 Analysis of the Secondary Endpoint

The safety of the treatment will be monitored, and any toxicities identified will be reported by type and grade. The feasibility and tolerability will be assessed and reported descriptively.

In each cohort, the fraction of patients who experience a response (PR + CR) will be reported along with 80% and 95% two-sided confidence intervals.

Overall survival will be calculated from the on-study date using the Kaplan-Meier method.

10.4.4 Safety analysis

The safety of the treatment will be monitored, and any toxicities identified will be reported by type and grade.

10.4.5 Baseline Descriptive Statistics

Baseline demographic characteristics will be reported.

10.4.6 Planned Interim Analyses

There are no planned interim analyses for efficacy.

10.4.7 Sub-group analyses

None are planned.

10.4.8 Tabulations of individual participant data

None.

10.4.9 Exploratory Analyses

The following objectives will result in descriptive or comparative analyses when adequate data exist to perform them:

- To evaluate the bioactivity of the combination of trametinib plus HCQ against the MEK1/2 and autophagy pathways by immunohistochemistry.
- To measure changes in immune parameters in the peripheral blood and tumors of patients with refractory KRAS mutation BTC treated with the combination of trametinib plus HCQ.
- To explore mechanism of primary and secondary resistance to the combination of trametinib plus HCQ in patients with refractory KRAS mutation BTC.
- To evaluate the relationship between the RR, OS and immune parameters, in patients with refractory KRAS mutation BTC treated with the combination of trametinib plus HCQ.
- Any exploratory evaluations which generate quantitative measures will be done using descriptive statistics including confidence intervals when appropriate. Any statistical tests performed for evaluation of exploratory objectives will be done without formal adjustment for multiple comparisons, but in the context of the number of tests performed.

11 COLLABORATIVE AGREEMENTS

11.1 Cooperative Research and Development Agreement (CRADA)

CRADA for this protocol is currently being negotiated between Thoracic & GI Malignancy Branch, NCI, NIH and Novartis, the manufacturer of trametinib.

12 HUMAN SUBJECTS PROTECTIONS

12.1 Rationale for Subject Selection

No individual who meets the criteria for eligibility will be excluded from participation based on their race, ethnicity, gender, or socioeconomic status. Particular attention will be made to acquire a broad and diversified population.

12.2 Participation of Children

Children (younger than 18 years) will not be included in this protocol due to the limited data on this combination in children and the different biology of childhood malignancy.

12.3 Participation of Subjects Unable to Give Consent

Adults unable to consent are excluded from enrolling in the protocol. However, it is possible that subjects enrolled in the protocol may permanently lose the capacity to consent for themselves during the course of this study. If a subject loses the capacity to consent during the course of the study for reasons unrelated to protocol participation and is receiving direct benefit from the study therapy in the opinion of the PI, the subject may be retained on the study therapy with the permission of the alternate decision maker. If the permanent loss of capacity is due to toxicity from the study therapy or disease progression, the participant will be removed from study therapy as required per protocol, but may be retained on study to be followed for safety reasons and/or overall survival as described in the Study Calendar 3.4. The follow-up procedures involve non-invasive, low risk studies, with the exception of scanning. Scanning during follow-up will be performed only in participants who are taken of treatment for reasons other than disease progression and only within 5 months of study initiation. These scans are clinically indicated. The benefit of a safety follow up would outweigh the risks of such procedures. All subjects will be offered the opportunity to fill in their wishes for research and care, and assign a substitute decision maker on the “NIH Advance Directive for Health Care and Medical Research Participation” form so that another

person can make decisions about their medical care in the event that they become incapacitated or cognitively impaired during the course of the study. Please see section **12.5** for the consent procedure.

12.4 Risk/Benefit Assessment for All Participants

12.4.1 Known Potential Risks

The primary risk to patients participating in this research study is from the toxicity of study drugs. All care will be taken to minimize study treatment side effects, but they can be unpredictable in nature and severity.

12.4.1.1 Risk of Biopsy

All care will be taken to minimize risks that may be incurred by tumor sampling. However, there are procedure-related risks (such as bleeding, infection, visceral injury, hematoma and death) that will be explained fully during informed consent. However, it may be noted that we have not experienced a single bleeding event in approximately 250 patients who have undergone liver biopsy procedures recently for other standard of care or research testing. The biopsies will be performed in interventional radiology.

12.4.1.2 Risks of Exposure to Ionizing Radiation

The study will involve radiation from the following sources:

- Up to 7 CT scans per year for disease assessment
- 2 CT scans for the collection of 2 mandatory biopsies

Subjects in this study may be exposed to approximately 9.3 rem per year. This amount is more than would be expected from everyday background radiation. Being exposed to excess radiation can increase the risk of cancer. The risk of getting cancer from the radiation exposure in this study is 0.9 out of 100 (0.9%) and of getting a fatal cancer is 0.5 out of 100 (0.5%).

12.4.1.3 Risks of CT Scans

In addition to the radiation risks discussed above, CT scans may include the risks of an allergic reaction to the contrast. Participants might experience hives, itching, headache, difficulty breathing, increased heartrate and swelling.

12.4.1.4 Risks of sedation

Biopsies will be done under sedation. Potential side effects of sedation include headache, nausea and drowsiness. These side effects usually go away quickly.

12.4.1.5 Risks of ophthalmologic exam

Risks of ophthalmologic exam include discomfort, blurry vision and light sensitivity.

12.4.1.6 Risks of Blood Collection

Risks of blood draws include pain and bruising in the area where the needle is placed, lightheadedness, and rarely, fainting. When large amounts of blood are collected, low red blood cell count (anemia) can develop. Up to the 170 ml of blood may be collected at any visit, but no more than 550 ml per 8 weeks period.

12.4.1.7 Risks of EKG

Risks include some minor skin irritation from the electrodes.

12.4.1.8 Risks of Echocardiogram

Risks include mild discomfort during the test.

12.4.1.9 Other Risks

Risks include the possible occurrence of any of a range of side effects which are listed in the Consent Document or this protocol document. Frequent monitoring for adverse effects will help to minimize the risks associated with administration of the study agents.

12.4.1.10 Risk of losing data

This includes the risk that data obtained during this study, including data related to genotype, DNA sequencing or risk for disease tendency or trait can be released to members of the public, insurers, employers, or law enforcement agencies. Although there are no plans to release results to the patients, family members or health care providers, this risk will be included in the informed consent document.

12.4.1.11 Risk of receiving unwanted information

Anxiety and stress may arise as a result of the anticipation that unwanted information regarding disease related DNA sequencing or disease tendencies, or misattributed paternity. Patients will be clearly informed that the data related to DNA sequencing and genetic analysis is coded, investigational and will not be shared with patients, family members or health care providers.

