5.2.4 Management of Results

Subjects will be contacted if a clinically actionable gene variant is discovered. Clinically actionable findings for the purpose of this study are defined as disorders appearing in the

American College of Medical Genetics and Genomics recommendations for the return of incidental findings that is current at the time of primary analysis. (A list of current guidelines is maintained on the CCR intranet: <https://ccrod.cancer.gov/confluence/display/CCRCRO/Incidental+Findings+Lists>). Subjects will be contacted at this time with a request to provide a blood sample to be sent to a CLIA certified laboratory. If the research findings are verified in the CLIA certified lab, the subject will be offered the opportunity to come to NIH (at our expense) to have genetic education and counseling to explain this result. If the subject does not want to come to NIH, a referral to a local genetic healthcare provider will be provided (at their expense).

This is the only time during the course of the study that incidental findings will be returned. No interrogations regarding clinically actionable findings will be made after the primary analysis.

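### Sections 12.4.1.10 and 12.4.1.11 rule out returning genetic results without exception, while 5.2.4 commits the study to returning listed actionable variants

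*Combined protocol and SAP*

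**What the plan says.** Three places in the protocol deal with what happens to an individual patient's genetic results.

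- **Section 12.4.1.11**, on the risk of unwanted information, prescribes what patients hear: "Patients will be clearly informed that the data related to DNA sequencing and genetic analysis is coded, investigational", and that the data "will not be shared with patients, family members or health care providers".
- **Section 12.4.1.10**, on the risk of losing data, says in passing that "there are no plans to release results to the patients, family members or health care providers".
- **Section 5.2.4**, on management of results, opens with "Subjects will be contacted if a clinically actionable gene variant is discovered". It defines actionable by reference to the ACMG incidental-findings recommendations in force when the primary analysis is done. The subject is asked for a new blood sample for a CLIA laboratory. "If the research findings are verified in the CLIA certified lab", then "the subject will be offered the opportunity to come to NIH (at our expense) to have genetic education and counseling to explain this result". For a subject who does not want to travel, "a referral to a local genetic healthcare provider will be provided". The section adds that incidental findings are returned on this one occasion only.

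Neither risk section refers to 5.2.4 or carries an exception for it.

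**The concern.** Section 5.2.4 is an operating procedure with a trigger, a confirmation step and a counseling step. The two risk sections describe a study in which no such procedure exists. Section 12.4.1.11 matters most, because it is an instruction about what patients are to be told.

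If the consent discussion follows 12.4.1.11 literally, patients agree to sequencing on the understanding that nothing will come back to them, and some may later be contacted. Section 5.2.4 describes no step at which a subject states a preference about contact, so a patient told to expect no results has no evident occasion to raise it. The heading of 12.4.1.11 names the very risk that 5.2.4 creates, yet its text answers that risk by saying nothing will be shared.

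The sequencing is planned study-wide. Section 5.2.3 plans whole exome sequencing on both tumor and blood, and the study calendar in 3.4 places the research blood for it at baseline. Inherited variants can therefore be detected.

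**Working it through.** No arithmetic applies, and the plan gives no figure to reproduce. The check is to take each outcome that 5.2.4 allows and ask whether the statements in 12.4.1.10 and 12.4.1.11 remain true.

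| Situation | Under 5.2.4 | Under 12.4.1.10 and 12.4.1.11 | Agree? |
|---|---|---|---|
| Sequencing output that is not a variant for a disorder on the ACMG list | No contact described | Not released, not shared | Yes |
| Listed variant found at the primary analysis | Subject contacted, blood sample requested | Not released, not shared | No |
| Listed variant verified by the CLIA laboratory, subject comes to NIH | Result explained in counseling | Not released, not shared | No |
| Listed variant verified, subject does not come to NIH | Referral to a local genetic provider | Not released or shared with patients or health care providers | No |
| Listed variant not verified | No explanation of a result described, but contact has already happened | Not released, not shared | No, as to the contact |
| Any time after the primary analysis | No further search for actionable findings | Not released, not shared | Yes |

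Three points follow.

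1. **The conflict begins at first contact.** The research finding itself triggers the contact. A request for a confirmatory sample already tells the subject that something was found, before any clinical result exists.
2. **It reaches providers as well as patients.** Both risk sections name health care providers among those who will not receive results. Section 5.2.4 does not spell out what the local provider is given, but the referral is offered in place of the NIH visit that would explain the result, so it makes little sense unless that provider can discuss it. An exception that mentioned patients alone would leave this part unresolved.
3. **It is confined to the listed disorders.** What must be current at the primary analysis is the ACMG recommendation. Everything outside it is treated alike in all three sections.

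On size: section 10.2 plans 17 patients with an accrual ceiling of 30, so the risk wording applies to at most that many. The conflict takes practical effect only for those with a listed variant. The documents do not say how common that is, and no figure is assumed here.

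**The case against.** The best defense is that 12.4.1.11 concerns data that are coded and investigational, whereas the result explained under 5.2.4 comes from a fresh sample verified in a certified laboratory. On that reading only the research data are withheld, and a clinical result is a different thing. This softens the clash but does not remove it, because the contact is prompted by the research data and 12.4.1.11 draws no such line. Nor does it help 12.4.1.10, which says no release of results is planned when 5.2.4 is such a plan.

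It is fair to add that 12.4.1.10 is the weaker support. Its subject is disclosure to the public, insurers, employers or law enforcement, and the remark about release is a subordinate clause. Section 12.4.1.11 carries the point.

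Four stronger readings are tempting, and the documents do not support them.

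- **A reader might infer that the risk text is false throughout.** It is incomplete: it is right for all sequencing output except the listed variants.
- **A reader might infer that one of the two provisions cannot be carried out.** Section 5.2.4 can be followed exactly as written. It is 12.4.1.11 that needs an exception.
- **A reader might infer that patients have been misinformed, or that consent to the exome work is defective.** The consent form is not among the documents reviewed and may already state the exception.
- **A reader might infer that an actionable finding would be withheld.** Section 5.2.4 is worded as mandatory, and nothing suggests that staff would let a sentence in the risk section override it.

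**Conclusion.** The inconsistency is real and can be confirmed from the text alone. When the plan is followed, the disclosure statement in 12.4.1.11, and the matching remark in 12.4.1.10, are untrue for one defined class of findings. It is minor: a correction that is nice to have in the human-subjects text, with no bearing on the primary endpoint, sample size, error rates or any analysis.

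The conclusion rests on 5.2.4 being the sponsor's actual intention. That is the natural reading, since it is the specific and procedural section. Any harm to patients is conditional on the consent discussion or form repeating the unqualified statement, which cannot be checked here.

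**What to change.** Add to both 12.4.1.10 and 12.4.1.11 the exception that 5.2.4 already defines. Suggested content: research sequencing results are not shared with patients, family members or providers, except that a variant for a disorder on the ACMG incidental-findings recommendations current at the primary analysis leads to contact with the subject, a request for a blood sample for CLIA confirmation and, if the finding is verified, counseling at NIH or referral to a local genetic provider. In 12.4.1.11, also describe the possibility of receiving such a result as a risk in its own right.

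Then compare the consent form with the revised text. If it already carries the exception, only the protocol needs changing. If the sponsor does not intend to return results, 5.2.4 is the section to revise. In either case the three sections should be reconciled.

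The cost is about two sentences in the risk section and one check of the consent form. The protocol's statement of compliance requires IRB approval for protocol amendments and consent changes, so the correction is best made before the primary analysis, when contact under 5.2.4 could begin.

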12.4.2 Known Potential Benefits

The study drug may help to control the disease. The results may help the investigators learn more about the disease and develop new treatments for patients with this disease

12.4.3 Assessment of Potential Risks and Benefits

BTC treatment needs improved therapy options. Preclinical studies suggest that study therapy may have tremendous anti-tumor efficacy.

A number of clinically appropriate strategies to minimize risks to patients have been built into the protocol through the means of inclusion/exclusion criteria, monitoring strategies, and management guidelines. Overall, the potential benefit of the study treatment in subjects with BTC outweigh the risks associated with study drugs.

The potential benefit to a patient that participates in this study is better control of their tumor growth and disease recurrence which may or may not have a favorable impact on symptoms and/or survival.

Potential adverse reactions attributable to the administration of the study drug utilized in this trial are discussed in Sections **1.2.5.2 and 1.2.6.2**. All care will be taken to minimize side effects, but they can be unpredictable in nature and severity.

12.5 Consent Process and Documentation

The informed consent document will be provided as a physical or electronic document to the participant or consent designee(s) as applicable for review prior to consenting. A designated study investigator will carefully explain the procedures and tests involved in this study, and the

associated risks, discomforts and benefits. In order to minimize potential coercion, as much time as is needed to review the document will be given, including an opportunity to discuss it with friends, family members and/or other advisors, and to ask questions of any designated study investigator. A signed informed consent document will be obtained prior to entry onto the study.

The initial consent process as well as re-consent, when required, may take place in person or remotely (e.g., via telephone or other NIH approved remote platforms used in compliance with policy, including HRPP Policy 303) per discretion of the designated study investigator and with the agreement of the participant/consent designee(s). Whether in person or remote, the privacy of the subject will be maintained. Consenting investigators (and participant/consent designee, when in person) will be located in a private area (e.g., clinic consult room). When consent is conducted remotely, the participant/consent designee will be informed of the private nature of the discussion and will be encouraged to relocate to a more private setting if needed.

Consent will be documented with required signatures on the physical document (which includes the printout of an electronic document sent to participant) or as described below, with a manual (non-electronic) signature on the electronic document. When required, witness signature will be obtained similarly as described for the investigator and participant.

Manual (non-electronic) signature on electronic document:

When a manual signature on an electronic document is used for the documentation of consent at the NIH Clinical Center, this study will use the following to obtain the required signatures:

- Adobe platform (which is not 21 CFR Part 11 compliant); or,
- iMedConsent platform (which is 21 CFR Part 11 compliant)

During the consent process, participants and investigators will view individual copies of the approved consent document on screens at their respective locations (if remote consent); the same screen may be used when in the same location but is not required.

Both the investigator and the subject will sign the document using a finger, stylus or mouse.

Note: Refer to the CCR SOP PM-2, Obtaining and Documenting the Informed Consent Process for additional information (e.g., verification of participant identity when obtaining consent remotely) found [here](#).

12.5.1 Consent Process for Adults Who Lack Capacity to Consent to Research Participation

For participants addressed in section **12.3**, an LAR will be identified consistent with Policy 403 and informed consent obtained from the LAR, as described in Section **12.5**

13 REGULATORY AND OPERATIONAL CONSIDERATIONS

13.1 Study Discontinuation and Closure

This study may be temporarily suspended or prematurely terminated if there is sufficient reasonable cause. Written notification, documenting the reason for study suspension or termination, will be provided by the suspending or terminating party to study participants. If the study is prematurely terminated or suspended, the Principal Investigator (PI) will promptly inform study participants, the Institutional Review Board (IRB), and sponsor and will provide the reason(s) for the termination or suspension. Study participants will be contacted, as applicable, and be informed of changes to study visit schedule.

Circumstances that may warrant termination or suspension include, but are not limited to:

- Determination of unexpected, significant, or unacceptable risk to participants
- Demonstration of efficacy that would warrant stopping
- Insufficient compliance to protocol requirements
- Data that are not sufficiently complete and/or evaluable
- Determination that the primary endpoint has been met
- Determination of futility

Study may resume once concerns about safety, protocol compliance, and data quality are addressed, and satisfy the sponsor, IRB and as applicable, Food and Drug Administration (FDA).

13.2 Quality Assurance and Quality Control

The clinical site will perform internal quality management of study conduct, data and biological specimen collection, documentation and completion. An individualized quality management plan will be developed to describe a site's quality management.

Quality control (QC) procedures will be implemented beginning with the data entry system and data QC checks that will be run on the database will be generated. Any missing data or data anomalies will be communicated to the site(s) for clarification/resolution.

Following written Standard Operating Procedures (SOPs), the monitors will verify that the clinical trial is conducted and data are generated and biological specimens are collected, documented (recorded), and reported in compliance with the protocol, International Conference on Harmonisation Good Clinical Practice (ICH GCP), and applicable regulatory requirements (e.g., Good Laboratory Practices (GLP), Good Manufacturing Practices (GMP)).

The investigational site will provide direct access to all trial related sites, source data/documents, and reports for the purpose of monitoring and auditing by the sponsor, and inspection by local and regulatory authorities.

